8.4. Clinical Laboratory Tests

Laboratory test results will be presented in standard international (SI) units.

Summary statistics for chemistry, hematology, and urinalysis laboratory tests will be presented at baseline and each visit that this is measured. Laboratory values and changes from baseline to each visit will be summarized using descriptive statistics. Listings of all individual participants' laboratory tests will be presented.

Shifts (below, within, and above the normal range) from baseline to each visit that this is measured will be summarized using participant counts.

Summaries of potentially clinically significant abnormal values will include all postbaseline values (including scheduled, unscheduled, and early termination visits). The incidence of potentially clinically significant abnormal values will be summarized for laboratory variables using descriptive statistics with the criteria specified in [Table 6](#).

Table 6: Criteria for Potentially Clinically Significant Laboratory Values

Test Category	Test	Criterion value
Serum chemistry	ALT	$>5 \times \text{ULN}$ $>5 \times \text{BL}$ if BL is abnormal ($> \text{ULN}$)
	AST	$>5 \times \text{ULN}$ $>5 \times \text{BL}$ if BL is abnormal ($> \text{ULN}$)
	ALP	$>5 \times \text{ULN}$ $>5 \times \text{BL}$ if BL is abnormal ($> \text{ULN}$)
	Creatinine	$>3 \times \text{ULN}$ $>3 \times \text{BL}$ if BL is abnormal ($> \text{ULN}$)
	Bilirubin (total)	$>3 \times \text{ULN}$ $>3 \times \text{BL}$ if BL is abnormal
	Potassium	$<3.0 \text{ mmol/L}$ $>6.0 \text{ mmol/L}$
	Sodium	$<120 \text{ mmol/L}$ $>155 \text{ mmol/L}$
	Calcium	Corrected serum calcium of $>12.5 \text{ mg/dL}$ Corrected serum calcium of $<7.0 \text{ mg/dL}$
	Phosphate	$<1.4 \text{ mg/dL}$
Hematology	Hemoglobin	$<8.0 \text{ g/dL}$ and/or decrease of 3.0 g/dL from BL $> \text{ULN} + 4.0 \text{ g/dL}$
	WBC counts	$<2.0 \times 10^9/\text{L}$ $>100 \times 10^9/\text{L}$
	Neutrophil	$<0.5 \times 10^9/\text{L}$
	Lymphocyte	$<0.5 \times 10^9/\text{L}$
	Platelet counts	$<50 \times 10^9/\text{L}$
Urinalysis	HGB	≥ 2 unit increase from BL
	Glucose	≥ 2 unit increase from BL
	Ketones	≥ 2 unit increase from BL
	Total protein	≥ 2 unit increase from BL

ALP=alkaline phosphatase; ALT=alanine aminotransferase; ANC=absolute neutrophil count AST=aspartate aminotransferase; BL = baseline; BUN=blood urea nitrogen; GGT=gamma-glutamyl transpeptidase; HGB=hemoglobin; LDH=lactate dehydrogenase; ULN=upper limit of normal range; WBC=white blood cell.

8.4.1. Liver-Related Laboratory Tests

Maximum post-baseline elevation in ALT, AST and bilirubin will be summarized as incidence and shift tables using the criteria specified in [Table 7](#).

Table 7: Liver-Related Laboratory Tests Criteria

Test	Criterion Value
ALT	>3 x ULN
	>5 x ULN
	>10 x ULN
	>20 x ULN
AST	>3 x ULN
	>5 x ULN
	>10 x ULN
	>20 x ULN
ALT or AST	>3 x ULN
	>5 x ULN
	>10 x ULN
	>20 x ULN
Bilirubin (total)	≥2 x ULN
Hy's Law	{ALT ≥3 x ULN or AST ≥3 x ULN} and {bilirubin (total) ≥2 x ULN} and {ALP <2 x ULN}

Incidence of participants meeting laboratory criteria for Hy's Law, i.e.

{ALT ≥3 x ULN or AST ≥3 x ULN} and {bilirubin (total) ≥2 x ULN} and {ALP <2 x ULN}, will be listed.

8.4.2. Other Clinical Laboratory Tests

Other clinical laboratory tests results will be presented in data listings.

8.5. Vital Signs and Weight

Summary statistics for pulse, systolic and diastolic blood pressure, respiratory rate, body temperature, and weight will be presented at baseline and each visit that this is measured. Vital signs values and changes from baseline to each visit will be summarized using descriptive statistics.

Summaries of potentially clinically significant abnormal values will include all postbaseline values (including scheduled, unscheduled, and early termination visits). The incidence of potentially clinically significant abnormal values will be summarized using descriptive statistics with the criteria specified in [Table 8](#).

[Table 8](#) specifies the criteria for identifying vital signs as potentially clinically significant abnormal values. Note that to qualify as potentially clinically significant abnormal, a value needs to meet both criteria below, i.e., have a value beyond the criterion value and a change of at least the magnitude specified in the change relative to baseline column.

Table 8: Criteria for Potentially Clinically Significant Vital Signs

Vital Sign	Criterion value	Change relative to baseline
Pulse	≥ 120 bpm	Increase of ≥ 15 bpm
	≤ 50 bpm	Decrease of ≥ 15 bpm
Systolic blood pressure	≥ 180 mm Hg	Increase of ≥ 20 mm Hg
	≤ 90 mm Hg	Decrease of ≥ 20 mm Hg
Diastolic blood pressure	≥ 105 mm Hg	Increase of ≥ 15 mm Hg
	≤ 50 mm Hg	Decrease of ≥ 15 mm Hg
Respiratory rate	<10 breaths/min	
Body temperature	$\geq 38.3^{\circ}\text{C}$	Change of $\geq 1.1^{\circ}\text{C}$

bpm=beats per minute

Maximum post-baseline changes in weight will be summarized using the criteria specified in [Table 9](#). Exclusion of participants with a baseline weight $\geq 100\text{kg}$ and/or BMI ≥ 30 at baseline from this analysis will be discussed in the blinded data review meeting prior to DBL and unblinding.

Table 9: Criteria for Weight Increase or Decrease

Test	Criterion Value
Weight	Increase of $\geq 5\%$ from BL
	Increase of $\geq 10\%$ from BL
	Decrease of $\geq 5\%$ from BL
	Decrease of $\geq 10\%$ from BL

BL = baseline

8.6. **Electrocardiography**

Shifts (normal, abnormal not clinically significant, and abnormal clinically significant) from baseline to each visit that this is measured, and from baseline to overall (anytime) will be summarized using participant counts for the investigator interpretation. For overall result interpretation the worst postbaseline finding for the participant (the abnormal finding if there are both normal and abnormal findings) will be used in the summaries.

Summary statistics for ECG variables will be presented at baseline and each visit that it is measured. Actual values and changes from baseline to each visit will be summarized using descriptive statistics.

The incidence of potentially clinically significant abnormal values will be summarized using descriptive statistics with the criteria specified in [Table 10](#). Note that to qualify as potentially clinically significant abnormal, a value needs to meet both criteria below, if applicable: e.g., have a value beyond the criterion value and a change of at least the magnitude specified in the change relative to baseline column. A listing of potentially clinically significant ECG results will be presented.

Table 10: Criteria for Potentially Clinically Significant Abnormal ECG

ECG Test	Criterion Value	Change Relative to Baseline
PR Interval	≥200 msec	Increase of at least 25% from baseline
QRS Duration	≥110 msec	Increase of at least 25% from baseline
QTcF Interval	≥450 msec and <500 – male or ≥460 msec and <500 – female	≥30 and <60 msec increase from baseline
	≥450 msec and <500 – male or ≥460 msec and <500 – female	≥60 msec increase from baseline
	≥500 msec	≥30 and < 60 msec increase from baseline
	≥500 msec	≥60 msec increase from baseline

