8. SAFETY ANALYSIS

8.1. General

The safety analysis set will be used for all safety analyses. Summaries will be presented by treatment and pooled TEV-45874, separately by indication (UC or CD) and pooled (UC and CD). The summaries will include participants in the 1800 mg treatment group that were randomized prior to PA03Rev01.

If an indication is stopped for safety reasons (see Section 13.1), pooled analyses of UC and CD will not be presented.

Safety listings will include all data collected, starting from screening. Safety summary tables will include all treatment-emergent data, ie, data collected from first day of trial drug until the end of the trial (including the FU period), unless specified otherwise.

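### Table 10 counts a QTcF result only when an absolute limit and a change limit are both met, so no output counts participants with a value ≥500 msec or a rise ≥60 msec as such

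*SAP*

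**What the plan says.** SAP Section 8.6 (Electrocardiography) sets a joint rule for ECG values: "a value needs to meet both criteria below, if applicable: e.g., have a value beyond the criterion value". The same sentence adds a second condition, that the shift from baseline must be no smaller than the size given in the table's other column. Table 10 then has four QTcF rows, formed by crossing two absolute bands with two change bands:

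- absolute bands: "≥450 msec and <500 – male or ≥460 msec and <500 – female", and 500 msec or more;
- change bands: "≥30 and <60 msec increase from baseline", and "≥60 msec increase from baseline".

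The threshold count rests on these rows: "The incidence of potentially clinically significant abnormal values will be summarized using descriptive statistics with the criteria specified in" Table 10. The only ECG listing that Section 8.6 names rests on the same definition: "A listing of potentially clinically significant ECG results will be presented".

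Three other statements bear on the point. Section 8.6 also summarises actual ECG values and changes by visit, and shifts in the investigator's interpretation. Section 4.1 includes the minimum and maximum among the descriptive statistics. Section 8.1 says of listings in general: "Safety listings will include all data collected, starting from screening".

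**The concern.** Table 10 uses 500 msec and 60 msec as its own highest bands, yet neither is ever counted alone. A participant can pass one of them and match no row because the other limit is not met. The resulting order is odd. A man going from 420 to 450 msec (+30) is counted. A man going from 360 to 440 msec (+80) is not, and neither is a participant going from 495 to 520 msec (+25).

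Change from baseline in 12-lead ECG findings is a stated safety measure under the secondary objectives (Section 1.1). Table 10 is the only QTcF threshold table in the SAP. If it reports zero, a reader may conclude that nobody reached 500 msec or rose by 60 msec, and the table cannot support that conclusion.

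**Working it through.** The SAP gives no figure of its own to reproduce here. The check is the row logic, followed by an illustration under stated assumptions.

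**Inputs.** The joint rule and the four QTcF rows come from Section 8.6 and Table 10. Baseline is the mean of the screening triplicate (Section 4.2.2). Let *b* be baseline, *v* the post-baseline value, *d* = *v* − *b*, and *L* = 450 (male) or 460 (female).

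**Rows as conditions.** A result is counted if any one of these holds:

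1. *L* ≤ *v* < 500 and 30 ≤ *d* < 60
2. *L* ≤ *v* < 500 and *d* ≥ 60
3. *v* ≥ 500 and 30 ≤ *d* < 60
4. *v* ≥ 500 and *d* ≥ 60

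The four rows together reduce to *v* ≥ *L* and *d* ≥ 30. The rule's qualifier about applicability exempts no QTcF row, because both columns are filled in all four. Table 8 shows how this SAP writes a single-criterion row: the change cell for respiratory rate is empty.

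**Gap 1, *d* ≥ 60 but not counted.** This requires *v* < *L*, so *b* = *v* − *d* < *L* − 60, which is 390 (male) or 400 (female). In whole msec the highest such baselines are 389 and 399.

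**Gap 2, *v* ≥ 500 but not counted.** This requires *d* < 30, so *b* = *v* − *d* > 500 − 30 = 470. In whole msec the lowest such baseline is 471, and the largest rise is 29.

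A check of baseline and post-baseline pairs on a 1-msec grid gave the same limits. Examples:

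| Sex | Baseline | Value | Rise | Counted? |
|---|---|---|---|---|
| Male | 385 | 449 | 64 | No |
| Male | 389 | 449 | 60 | No |
| Male | 390 | 450 | 60 | Yes |
| Female | 399 | 459 | 60 | No |
| Female | 400 | 460 | 60 | Yes |
| Either | 471 | 500 | 29 | No |
| Either | 470 | 500 | 30 | Yes |
| Either | 495 | 520 | 25 | No |

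**Illustration for gap 1.** The SAP gives no QTcF distribution. Assume that male baseline QTcF is normal with SD 20 msec and that the rise is independent of baseline. A man who rises by exactly *d* ≥ 60 is missed when *b* < 450 − *d*, so the share missed is Φ((450 − *d* − mean)/20).

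| Assumed mean (msec) | Rise of 60 (cut-off 390) | Rise of 70 (cut-off 380) |
|---|---|---|
| 400 | Φ(−0.5) = 31% | Φ(−1.0) = 16% |
| 410 | Φ(−1.0) = 16% | Φ(−1.5) = 7% |
| 420 | Φ(−1.5) = 7% | Φ(−2.0) = 2% |

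These shares are conditional on such a rise having occurred. A rise of exactly 60 msec gives the largest share of any rise of 60 or more.

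**The case against.** The joint rule looks deliberate. Section 8.5 applies the same rule to vital signs, and the aim is to identify values that are both abnormal and changed. On that reading a man at 449 msec is not abnormal, and leaving him out follows from the definition. This stands as far as it goes: the SAP does not contradict itself here, and the joint rows have a purpose. It does not explain why the table's own top bands are never counted separately. Elsewhere the SAP does separate such criteria: Table 6 joins hemoglobin's low limit and its decrease from baseline by an and/or, and Table 7 counts each liver threshold as well as the Hy's Law combination.

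A reader might infer more than the SAP supports in three respects.

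- **That these participants appear in no listing.** Section 8.1 gives safety listings a scope of all data collected. Section 8.6 names no full ECG listing, so one is not certain, but its absence cannot be asserted either. What can be said is that these results are unflagged in the listing of potentially clinically significant ECG results.
- **That the other ECG output consists of means only.** By-visit summaries of values and changes include maxima, so a value of 500 msec or a rise of 60 msec could be seen by visit and group. Interpretation shifts, including the worst post-baseline finding, are also tabulated. The ECG safety measure is therefore not left unreported. None of these outputs gives the number of participants beyond a QTcF threshold.
- **That 31%, 16% or 7% of large rises will be missed.** Those figures rest on an assumed distribution and apply only to men with a rise of exactly 60 msec. The share falls for larger rises.

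Gap 2 also needs a screening mean above 470 msec. ECG eligibility limits are not in the SAP, so that group may be very small or empty.

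**Conclusion.** The point holds as a gap in safety reporting. As Table 10 is written, a rise of 60 msec or more ending below 450 (male) or 460 (female) msec, and a value of 500 msec or more with a rise under 30 msec, are absent from the incidence table and unflagged in the matching listing. No planned output counts participants with either result. This follows from the row logic alone and needs no assumption.

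The practical size is unknown. The SAP gives neither the baseline QTcF distribution nor the expected number of large rises. No efficacy conclusion, sample size or safety stopping criterion is affected. The change is worth making because it is cheap and lets the only QTcF threshold table report the bands that it treats as most severe.

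**What to change.** In Table 10, add QTcF rows that stand on one criterion each:

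- value ≥450 msec (male) or ≥460 msec (female), and <500 msec;
- value ≥500 msec;
- increase ≥30 and <60 msec;
- increase ≥60 msec.

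Keep the four joint rows as additional rows, and state in Section 8.6 that the both-criteria rule applies to the joint rows only. Include in the ECG listing any participant with a post-baseline QTcF ≥500 msec or an increase ≥60 msec.

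With these rows, every result in both gaps is counted. The cost is a short wording change, four table rows and probably a few more listed participants. No new data are needed.

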8.7. Concomitant Medications or Therapies

Concomitant therapies and medications, including medications that are taken on an as needed basis and occasional therapies, will be monitored during the trial. Details of prohibited medications may be found in Section 5.6.4 of the trial protocol. All concomitant medications will be coded using the WHO Drug dictionary.

Any medication or therapies initiated on the same date of study treatment exposure will not be considered as concomitant medications or therapies. This also applies for the same year or month if other specific information is missing. In addition, any medications or therapies that are recorded but have completely missing start and stop dates will not be considered concomitant. A separate listing will be provided to account for these medications or therapies recorded in the study, but not considered concomitant.

The incidence of concomitant therapies and medications will be summarized using descriptive statistics by therapeutic class category and PT. Participants are counted only once in each therapeutic class, and only once in each PT category. Concomitant therapies and medications will include all medications taken during the treatment period. Any medications or therapies started after the treatment period will be included in a separate listing.

For patients who early terminate, any medication that started prior to the ET visit or up to 2 weeks after last dose of IMP, whichever comes first, is considered concomitant. Any medication that started at or after ET visit is not considered concomitant and will not be included in the summary table but will be included in the listing and footnoted accordingly.

8.8. Other Safety Assessments

8.8.1. Local Tolerability

Local tolerability at the injection site (erythema, ecchymosis, induration, tenderness, warmth, and swelling) will be assessed using standardized scales as described in Table 8 of the trial protocol.

Local tolerability response will be summarized at each visit that this is measured using descriptive statistics as categorical data.

8.8.2. Injection Pain Intensity Assessment

Injection site pain will be reported using a standardized 11-point pain intensity numerical response scale (NRS-11) where 0 is “No pain” and 10 is the “Worse possible pain”

The injection site pain intensity assessment will be summarized at each timepoint and visit that it is measured using descriptive statistics as categorical data. The timepoints during IMP administration and ‘after the completion of IMP administration’ will be presented as one timepoint, based on the worst assessment.

9. TOLERABILITY VARIABLES AND ANALYSIS

Tolerability will be assessed by the number (%) of participants who withdraw from the trial due to adverse events. Tolerability is summarized with participant disposition.

If more than 10% of participants withdraw from the trial due to adverse events, a Kaplan-Meyer analysis of time to withdrawal will be performed, separately by indication (UC or CD) and pooled (UC and CD).

In case that any dose is stopped for safety reasons (see Section 13.1), the tolerability analysis will be repeated excluding the dose(s) that was (were) stopped.

10. IMMUNOGENICITY ANALYSIS

Results of immunogenicity assessments will be listed and summarized using descriptive statistics. Immunogenicity summaries will be presented by indication and treatment group, including pooled TEV-48574.

Participants with pre-existing ADAs correspond to participants with ADAs present at baseline (prior to first dose of IMP). Participants with missing ADA sample at baseline will be considered as without pre-existing ADA.

ADA status at each post-baseline visit will be classified to one of 3 categories:

- Treatment-emergent ADA positive:
 - the participant has a positive ADA sample (after 1st dose of IMP) but not at baseline (prior to first dose of IMP), or
 - the participant had a positive ADA sample at baseline (prior to first dose of IMP) and at the visit (after 1st dose of IMP), with at least a 4-fold increase in titer level.
- ADA negative: the participant does not have a positive ADA sample at the visit
- Inconclusive: otherwise

ADA status of each participant (anytime post-baseline) will be classified as follows:

- Participants with treatment-emergent ADA correspond to participants with at least one treatment-emergent positive ADS sample.
- Participants with unclassified ADA correspond to patients with pre-existing ADAs that cannot be classified as treatment-emergent ADA because of missing titer(s) (ie, a positive ADA sample after first IMP administration in a participants with pre-existing ADA but with missing titer at this sample or at baseline).
- Participants without treatment-emergent ADA correspond to participants without treatment-emergent ADA and without any inconclusive sample after first IMP administration.
- Participants with inconclusive ADA are defined as participants which cannot irrefutably be classified as with or without treatment-emergent ADA.

ADA status at baseline, at each post-baseline visit, and overall (anytime post-baseline) will be summarized using descriptive statistics.

For ADA positive participants, titer level, and neutralizing ADA positive/negative will be summarized at each visit using descriptive statistics. In addition, the incidence of neutralizing ADA positive anytime will be summarized.

The kinetics of ADA response and the effect of positive immunogenicity findings on efficacy, safety, PK, and PD may be investigated, if applicable.

The immunogenicity analysis set will be used for immunogenicity analysis.

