	
 Clinical remission defined as score of rectal bleeding = 0 and stool frequency = 0 on the PRO2-UC scale at week 14 
The secondary efficacy endpoints to be measured in participants with moderate to severe CD are as follows:
 
 Clinical response defined as a ≥ 100-point decrease in Crohn's Disease Activity Index (CDAI) score from baseline at weeks 4, 8, 12 and 14 Clinical remission defined as a CDAI score < 150 at week 14 Clinical response defined as a decrease from baseline of at least 50% in PRO2 (PRO2-CD; abdominal pain and stool frequency) at week 14 Clinical remission defined as abdominal pain ≤ 1 and stool frequency ≤ 3 on the PRO2 scale at week 14 Endoscopic response defined as a decrease in modified multiplier (MM)-SES-CD of $> 50\%$ from baseline at week 14

A secondary objective of the trial is to evaluate the safety and tolerability of 3 different dose regimens of TEV-48574 sc administered Q2W in adult participants with IBD (moderate to severe UC or CD).
	
The safety and tolerability measures/parameters are as follows:
 
 Adverse events Change from baseline in clinical laboratory test results (serum chemistry, hematology, and urinalysis) Change from baseline in vital signs measurements (blood pressure, pulse rate, body temperature, and respiratory rate) Change from baseline in 12-lead electrocardiogram findings Participants who stopped the investigational medicinal product due to adverse events Local tolerability at the injection site

A secondary objective of the trial is to evaluate the immunogenicity of 3 different dose regimens of TEV-48574 sc administered Q2W in adult participants with IBD (moderate to severe UC or CD).
	
The immunogenicity endpoints for this trial are as follows:
 
 Treatment-emergent anti-drug antibody (ADA) at weeks 2, 4, 8, 14, and follow-up visit

Objectives	Endpoints
	
• Presence of neutralizing ADA in ADA positive participants at weeks 2, 4, 8, 14, and follow-up visit

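### Section 10 labels stable pre-existing ADA inconclusive although its own 4-fold rule settles the case, and its wording lets a missing sample count as ADA negative

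*SAP*

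**What the plan says.** Immunogenicity is a secondary objective in SAP Section 1.1, with the endpoint "Treatment-emergent anti-drug antibody (ADA) at weeks 2, 4, 8, 14, and follow-up visit".

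Section 10 sets the rule for visits: "ADA status at each post-baseline visit will be classified to one of 3 categories". The three are:

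- *Treatment-emergent positive*: a post-dose positive in someone not positive at baseline, or a positive at both times "with at least a 4-fold increase in titer level".
- *Negative*: "ADA negative: the participant does not have a positive ADA sample at the visit".
- *The remainder*: "Inconclusive: otherwise".

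At participant level there are four groups:

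- *With treatment-emergent ADA*: at least one treatment-emergent positive sample.
- *Unclassified*: pre-existing ADA that cannot be judged because a titre is missing.
- *Without treatment-emergent ADA*: "participants without treatment-emergent ADA and without any inconclusive sample after first IMP administration".
- *Inconclusive*: people who cannot be placed with certainty on either side.

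A missing baseline sample is explicitly treated as no pre-existing ADA. Section 10 has no matching sentence for a missing post-baseline sample. Section 4.3 restricts analyses to observed data unless that section itself says otherwise, and Section 4.1 allows a missing category in categorical summaries. Under Section 3.4, one reportable result is enough to enter the immunogenicity analysis set, and it need not be post-baseline.

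**The concern.** The visit rule has no place for a positive sample that is known not to be treatment-emergent. The commonest form of this is a pre-existing antibody whose titre stays roughly stable. The default sends it to inconclusive, and the participant rule carries the label to the whole trial period, even if every other visit is negative. The reader of the report would then see as undetermined some participants whose status the SAP's own criterion determines.

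The negative category has a different weakness. It is defined by not having a positive, when it should require a negative result. With no missing category in Section 10, a programmer can reasonably produce either of two tables: one that counts absent samples as negative, and one that leaves them out. The two differ in the negative percentage and in the denominator of every by-visit percentage.

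**Working it through.** The SAP states no ADA incidence, so there is no figure to reproduce. The check is to apply the Section 10 rules to every combination of baseline and visit result, reading the first treatment-emergent bullet as applying at the visit. TE means treatment-emergent positive.

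| Baseline | Visit negative | Visit positive, rise <4-fold | Visit positive, rise ≥4-fold | Visit positive, titre missing | No sample at visit |
|---|---|---|---|---|---|
| Negative | negative | TE | TE | TE | negative |
| Missing (treated as no pre-existing ADA) | negative | TE | TE | TE | negative |
| Positive, titre known | negative | **inconclusive** | TE | inconclusive | negative |
| Positive, titre missing | negative | inconclusive | inconclusive | inconclusive | negative |

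Four things follow from these 20 cells.

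1. Five cells are inconclusive. Four of them involve a missing titre, which the participant-level *unclassified* group already covers. Those four therefore meet both *unclassified* and *inconclusive*.
2. The fifth cell (bold) has both titres known and a rise below 4-fold. It is the only inconclusive cell that is not also *unclassified*, and it is the one that can be classified. The participant is excluded from *without* by the condition "without treatment-emergent ADA and without any inconclusive sample after first IMP administration" and lands in *inconclusive*, against that group's own definition.
3. All four cells with no sample read as negative. A participant with only a baseline result is in the analysis set and, on the literal wording, counts as without treatment-emergent ADA.
4. No TE cell depends on either defect. The number of treatment-emergent positives is the same before and after repair.

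To show what moves, take one active arm in one indication at the planned 40 participants (Section 2.5). Assume 4 treatment-emergent positives, e stable pre-existing positives (0 to 4) and m missing samples at the visit (0 to 8). The values 4, e and m are assumptions; the SAP gives none of them.

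- Literal wording: TE = 4/40 = 10.0% for any m. Negative = (40 − 4 − e)/40, which is 90.0%, 85.0% and 80.0% for e = 0, 2 and 4. Inconclusive = e/40 = 0%, 5.0% and 10.0%.
- Repaired rules: TE = 4/(40 − m), which is 10.0%, 11.1% and 12.5% for m = 0, 4 and 8. Not treatment-emergent = (40 − m − 4)/(40 − m) = 90.0%, 88.9% and 87.5%. Inconclusive = 0%.

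The numerator is 4 in every case.

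**The case against.** The strongest reply on missing samples is that Section 4.3 already governs them. Counting an absent sample as negative would be an imputation, and where Section 10 wants that, at baseline, it says so. This stands in part: the SAP does not order missing samples to be counted as negative. But the general text and the literal category definition point in different directions, and Section 10 does not settle it.

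A second reply is that these are descriptive labels with no test or decision attached, and that all results are listed, so a reader could re-tabulate. That is true and limits the consequence. It does not make the labels right.

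Three stronger readings are tempting, and the document does not support them.

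- A reader might infer that the treatment-emergent endpoint itself is miscounted. It is not: neither defect moves anyone into or out of that category.
- A reader might note that the first treatment-emergent bullet does not repeat that the positive must occur at the visit, and conclude that one positive carries to all visits. A later visit without a positive would then be both treatment-emergent positive and negative, which breaks the one-of-three rule. Only the visit-level reading is coherent.
- A reader might expect a large dilution at follow-up, because Section 2.1 excuses extension entrants from that visit. The SAP gives no rollover or positivity rate, and under Section 4.3 people with no observation at that visit would ordinarily not be in its denominator.

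**Conclusion.** The first part holds on the text: participants with stable pre-existing ADA and known titres are put in a category that the SAP reserves for people it cannot classify, and positives with a missing titre belong to two categories. The second part holds as an unresolved conflict between the wording of the negative status and Sections 4.1 and 4.3, not as a stated rule to impute.

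The effect is confined to the split between negative, without and inconclusive and, if missing samples are counted as negative, to the by-visit denominators. In the illustration, up to 10 percentage points of an arm move out of inconclusive, and the treatment-emergent visit percentage rises from 10.0% to at most 12.5%. Both shifts scale with assumed inputs, so the true size cannot be stated. The point deserves correction because it concerns the reporting of a secondary endpoint and the rules can be made consistent before unblinding at little cost.

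**What to change.** In SAP Section 10:

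1. Add a visit category *positive, not treatment-emergent*: positive at baseline and at the visit, both titres known, rise below 4-fold. At participant level, count these people under *without treatment-emergent ADA*, provided that no other sample is treatment-emergent or has an unresolved titre.
2. Define *ADA negative* as a reportable negative result at that visit.
3. Show missing samples separately, and use participants with a reportable result at the visit as the denominator of by-visit percentages.
4. Keep one category for positives that cannot be judged because a titre is missing, so that *unclassified* and *inconclusive* no longer overlap.

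The cost is a few lines of SAP text and the matching derivation code. No new samples or assays are needed.
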